## 4 STUDY DESIGN

### 4.1 OVERALL DESIGN

This study is an adaptive phase 3, randomized, double-blind, placebo-controlled trial to evaluate the efficacy and safety of sarilumab in hospitalized adults with severe or critical COVID-19. The study will be conducted in Europe and other countries except in the United States (US) in up to 100 sites.

Patients will be randomized in a 2:2:1 allocation ratio to sarilumab 400 mg IV, sarilumab 200 mg IV, or placebo. The sarilumab 200 mg IV dose arm will be closed for patients enrolled after Amended Protocol 04 is implemented. Patients enrolled after implementation of Amended Protocol 04 will be randomized in a 2:1 allocation ratio to sarilumab 400 mg IV or placebo (Section 4.3). All patients will receive a single dose of study drug on Day 1. Patients may receive a second dose with study drug (based on the original treatment group assigned) 24 to 48 hours after the first dose, if

1. The Benefit Risk assessment by the investigator favors the administration of another dose of study drug without compromising safety (e.g., increase in LFTs, neutropenia)

AND

2. At least one of the following criteria is met:
  - Increase in fever or recurrence of fever compared to Day 1 OR
  - Increase or no change in FiO2 requirement compared to Day 1 OR
  - Requiring vasopressors, ECMO, or development of multi-organ dysfunction

The safety data from approximately the first 12 patients randomized (assuming a total of ~10 patients are dosed on the sarilumab doses of 200 mg IV or 400 mg IV) will be reviewed by an independent data monitoring committee (IDMC) after the last of these patients dosed reaches Day 7. Data on approximately the first 12 and 50 patients (regardless of severity of illness) with at least 7-days follow-up will be reviewed by the IDMC to determine if the study can continue with or without modification. Subsequently, the frequency of IDMC meetings will be determined following the first 2 IDMC meetings. In addition to these specific assessment times, the IDMC will actively monitor interim data to make recommendations about early study closure, changes to study arms, and/or the eligible patient population throughout the course of the study.

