#### **7.1.2 Temporary discontinuation**

Dose modification for an individual patient is not allowed.

Study drug discontinuation does not apply for this study.

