## 7.2 PARTICIPANT DISCONTINUATION/WITHDRAWAL FROM THE STUDY

### Individual Patient Stopping Rules

For an individual patient, infusion rate should be slowed or stopped if they have a suspected drug-related event of hypersensitivity (Grade 2 or higher) during the infusion. Patients who have an IV infusion stopped for a safety related issue will not continue with dosing nor receive a subsequent dose.

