## Analysis

All AEs reported in this study will be coded using the currently available version of the Medical Dictionary for Regulatory Activities (MedDRA®). Coding will be to lowest level terms. The preferred term (PT), and the primary system organ class (SOC) will be listed.

Summaries of all TEAEs by treatment group will include:

- The number (n) and percentage (%) of patients with at least 1 TEAE by SOC and PT
- TEAEs by severity, presented by SOC and PT
- TEAEs by relationship to treatment (related, not related), presented by SOC and PT
- Treatment-emergent AESIs (defined with a PT or a prespecified grouping)

Deaths and other SAEs will be listed and summarized by treatment group.

Treatment-emergent adverse events leading to permanent treatment discontinuation will be listed and summarized by treatment group.

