#### 10.3.4.1.1 Interruption of the Intravenous Infusion

The infusion should be interrupted if any of the following AEs are observed:

- Sustained/severe cough
- rigors/chills
- rash, pruritus (itching)
- urticaria (hives, welts, wheals)
- diaphoresis (sweating)
- hypotension
- dyspnea (shortness of breath)
- vomiting
- flushing

The reaction(s) should be treated symptomatically, and the infusion may be restarted at 50% of the original rate.

If investigators feel there is a medical need for treatment or discontinuation of the infusion other than described above, they should use clinical judgment to provide the appropriate response according to typical clinical practice.

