#### 10.3.4.1.2 Termination of the Intravenous Infusion

The infusion should be terminated and NOT restarted if any of the following adverse events occur:

- anaphylaxis\*
- laryngeal/pharyngeal edema
- severe bronchospasm
- chest pain
- seizure
- severe hypotension
- other neurological symptoms (confusion, loss of consciousness, paresthesia, paralysis, etc.)

- any other symptom or sign that, in the opinion of the investigator, warrants termination of the IV infusion

\*Consider anaphylaxis if the following is observed (37): acute onset of an illness (minutes to several hours) with involvement of the skin, mucosal tissue, or both (eg, generalized hives, pruritus or flushing, swollen lips-tongue-uvula) AND AT LEAST ONE OF THE FOLLOWING:

- Respiratory compromise (eg, dyspnea, wheeze-bronchospasm, stridor, reduced peak expiratory flow, hypoxemia)
- Reduced BP or associated symptoms of end-organ dysfunction (eg, hypotonia [collapse], syncope, incontinence).

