2.4.5.1 Analyses of adverse events

Generalities

The primary focus of adverse event reporting will be on treatment-emergent adverse events. Pretreatment and posttreatment adverse events will be described separately.

If an adverse event date/time of onset (occurrence, worsening, or becoming serious) is incomplete, an imputation algorithm will be used to classify the adverse event as pretreatment, treatment-emergent, or posttreatment. The algorithm for imputing date/time of onset will be conservative and will classify an adverse event as treatment emergent unless there is definitive information to determine it is pretreatment or posttreatment. Details on classification of adverse events with missing or partial onset dates are provided in [Section 2.5.3](#).

Adverse event incidence tables will be sorted by SOC internationally agreed order and HLGT, HLT, PT by alphabetic order. For adverse event incidence tables presented by SOC and PT, they will be sorted by the internationally agreed SOC order and by decreasing incidence of PTs based

on the Sarilumab 400 mg IV group within each SOC, for the number (n) and percentage (%) of patients experiencing an adverse event. Multiple occurrences of the same event in the same patient will be counted only once in the tables within a treatment phase. The denominator for computation of percentages is the safety population within each treatment group.

Analysis of all treatment-emergent adverse events

The following treatment-emergent adverse event summaries will be generated for the safety population.

- Overview of treatment-emergent adverse events, summarizing total number or number (%) of patients with any
 - Treatment-emergent adverse event
 - Serious treatment-emergent adverse event
 - Severe treatment-emergent adverse event
 - AESI
 - Treatment-emergent adverse event leading to death
 - TEAE leading to study drug interruption or discontinuation
- All treatment-emergent adverse event by primary SOC, HLT, and PT, showing the number (%) of patients with at least 1 treatment-emergent adverse event.
- All treatment-emergent adverse events by primary SOC and PT, showing the number (%) of patients with at least 1 treatment-emergent adverse event.
- All treatment-emergent adverse events by primary SOC, PT and CTC grade, showing the number (%) of patients with at least 1 treatment-emergent adverse event.

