- All treatment-emergent adverse events regardless of relationship and related by primary SOC and PT, showing the number (%) of patients with at least 1 treatment-emergent adverse event.
- All treatment-emergent adverse events leading to study drug interruption or discontinuation by Primary SOC and PT, showing the number (%) of patients with at least 1 treatment-emergent adverse event.

Analysis of all treatment emergent serious adverse event(s)

- All treatment-emergent serious adverse events by primary SOC and PT showing the number (%) of patients with at least 1 serious treatment-emergent adverse event.
- All treatment-emergent serious adverse events regardless of relationship and related to IMP, by primary SOC, and PT, showing the number (%) of patients with at least 1 treatment-emergent serious adverse event.

Analysis adverse event of special interest

Unless otherwise specified, AESI will be summarized during the TEAE period by prespecified-grouping (AE category of interest), showing the number (%) of participants, sorted by decreasing

frequency of PT. In addition, summary of TEAE of infusion reactions, ALT increase, and infection events will be provided.

Listings of all adverse events, serious adverse events and AESIs during the study will be provided.

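### SAP 2.4.5.1 pools infusion interruption with permanent discontinuation, so the by-arm permanent-discontinuation summary promised in Protocol 9.4.3.2.1 is not specified

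*Protocol*

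**What the plan says.** **Protocol, analysis commitment.** Under Analysis in Section 9.4.3.2.1, TEAEs "leading to permanent treatment discontinuation will be listed and summarized by treatment group". Section 9.4 describes itself as a summary and leaves the more detailed description to the SAP.

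**Protocol, the category itself.** Section 7.1.1 treats permanent and definitive discontinuation of study intervention as the same thing, expects it rarely, and requires every confirmed case to be recorded in the CRF. Section 7.1.2, headed Temporary discontinuation, adds: "Study drug discontinuation does not apply for this study".

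**Protocol, infusion handling.** Section 7.2 tells sites to slow or stop the infusion for suspected drug-related hypersensitivity of Grade 2 or higher, and continues: "Patients who have an IV infusion stopped for a safety related issue will not continue with dosing nor receive a subsequent dose". Section 10.3.4.1.1 covers interruption, after which "the infusion may be restarted at 50% of the original rate". Section 10.3.4.1.2 covers termination: "The infusion should be terminated and NOT restarted if any of the following adverse events occur".

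**SAP.** Section 2.4.5.1 lists "TEAE leading to study drug interruption or discontinuation" as a line of the TEAE overview, and then "All treatment-emergent adverse events leading to study drug interruption or discontinuation by Primary SOC and PT". Section 2.4.5 says that safety results are shown by treatment group. Permanent discontinuation on its own appears only in Section 2.4.5.7, as one of the events summarized by ADA status for the sarilumab group.

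**The concern.** An infusion that is paused, restarted at half rate and completed is a tolerability event. One that ends a patient's dosing is a different outcome. The protocol commits to reporting the second by arm. The SAP, which should be the more detailed document, merges the two. With only a pooled row, a reader of the study report cannot tell whether sarilumab ended treatment more often than placebo or merely caused more pauses. At stake is one promised safety contrast for an intravenous regimen that the protocol itself describes as carrying uncertainty (Section 2.3).

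**Working it through.** The check is mainly a comparison of text. The plan states no figure for this item, so there is none to reproduce.

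**Step 1. Promise against specification.**

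| Output | Permanent discontinuation alone? | By arm, with placebo? | Attributed to a TEAE? |
|---|---|---|---|
| Protocol 9.4.3.2.1 (promised) | Yes | Yes | Yes |
| SAP 2.4.5.1 overview | No, pooled | Yes | Yes |
| SAP 2.4.5.1 SOC/PT table | No, pooled | Yes | Yes |
| SAP 2.4.5.7 | Yes | No, by ADA status in sarilumab | Yes |
| SAP 2.4.3.2 compliance | No, first infusion completed or not | Yes | No |
| SAP 2.4.3.1 dosing listing | No, interruption and re-administration | Listing only | Partly |

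No SAP row matches the promised row in all three columns. Both by-arm TEAE outputs for this item (2 of 2) are pooled.

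**Step 2. What the pooled row can show.** In one arm, let I be the number of patients with an interruption, D the number with permanent discontinuation and B the number with both. The pooled count is I + D − B. Given only that count, D can be anything from 0 up to the count. Equal pooled counts in two arms are therefore compatible with different values of D, and unequal pooled counts with equal values.

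**Step 3. The unit of the shift.** A patient who is interrupted, restarted and completes the infusion adds 1 to the pooled row and 0 to a permanent-discontinuation row. That is 100/n percentage points in an arm of size n.

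- *All 400 treated at 2:2:1* (Protocol 9.2): 160, 160 and 80 for 400 mg, 200 mg and placebo.
- *Switch to 2:1 after about 200 randomized.* This is an assumption based on the planned interim size, because the documents do not give the actual switch point. 400 mg: 80 + 200 × 2/3 = 213.3. 200 mg: 80. Placebo: 40 + 200 × 1/3 = 106.7.

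| Arm | Calculation | Points per patient |
|---|---|---|
| 400 mg | 100/213.3 to 100/160 | 0.47 to 0.63 |
| 200 mg | 100/160 to 100/80 | 0.63 to 1.25 |
| Placebo | 100/106.7 to 100/80 | 0.94 to 1.25 |

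This is only the size of one reclassified patient. The documents give no rate of interruption or discontinuation, so it cannot be scaled to an expected total.

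**Step 4. How much the neighbouring outputs recover.** SAP 2.4.3.2 divides patients who completed the first infusion by patients who received study drug. Its complement counts incomplete first infusions by arm, and a patient who was interrupted, restarted and finished counts as compliant. It does not separate adverse events from other causes (SAP 2.4.3.1 names device problems and patient decision). It also does not cover a second infusion, or a decision to end dosing taken after a complete first infusion.

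**The case against.** The strongest case is that little is lost. Most patients receive one infusion, and Protocol 7.1.1 expects permanent discontinuation to be rare. SAP 2.4.3.2 gives first-infusion completion by arm, and SAP 2.4.3.1 summarizes the number of doses by arm. SAP 2.4.5.1 adds a summary of infusion reactions and listings of all adverse events, so the listing half of the promise is largely met. The missing row can be derived from collected data. The SAP's silence about a change in Sections 1.5 and 1.6 shows little, since both tables cover major changes only. All of this stands and keeps the point minor. What remains is that no TEAE-attributed, by-arm count of permanent discontinuation is specified, although the protocol says there will be one. Section 7.1.2 does not make the category empty: it sits under temporary discontinuation, while 7.1.1 provides for permanent discontinuation.

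Two stronger readings are tempting, and the documents do not support them.

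- *A reader might infer that Protocol 7.2 contradicts 10.3.4.1.1, or leaves a second dose unguarded after a reaction.* Section 7.2 contrasts slowing with stopping and says dosing does not continue, which naturally describes an ended infusion. Section 10.3.4.1 separates interruption from termination, and Section 8.3.6 refers to 10.3.4 for managing acute reactions. Restart after interruption is permitted, not required. Any second dose must first pass the investigator's benefit-risk condition in Section 4.1, whose examples are open-ended. Several signs on the interruption list also appear in the Grade 2 and 3 rows of Table 13. That is an overlap of names, because the 7.2 trigger also requires suspected drug-related hypersensitivity.
- *A reader might infer that the pooling in the SAP follows from the wording of 7.2.* Nothing in either document links them.

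**Conclusion.** The reporting gap holds on the text and is minor. Both by-arm SAP outputs pool two outcomes that the protocol separates, and the one unpooled output has no placebo comparison. The consequence is limited to safety tabulation. The primary and key secondary analyses, alpha and power are unaffected, and no dosing-safety fault is shown. The 0.47 to 1.25 points describe one hypothetical patient, with the end figures for each arm depending on an assumed switch point. They are not an estimate of bias. The conclusion rests on the SAP text supplied; separate table shells, if they exist, might already split the category.

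**What to change.** In SAP 2.4.5.1, replace the pooled category in both the overview and the SOC/PT table with two rows by treatment group:

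- (a) TEAE leading to infusion interruption with re-administration;
- (b) TEAE leading to permanent (definitive) discontinuation, as recorded in the CRF under Protocol 7.1.1.

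Add a listing for (b). A patient may count in both rows. Tie (b) to Protocol 7.1.1 rather than to the word used in 7.2, so that a decision to end dosing after a completed first infusion is included. Infusions interrupted and not re-administered should be reconciled with the discontinuation record so that they do not fall between the rows.

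The cost is two table shells and one listing. No new data are needed: SAP 2.4.3.1 already uses interruption and re-administration, and Protocol 7.1.1 already requires definitive discontinuation to be recorded. This assumes that the CRF links adverse events to the action taken, which the pooled tables already presuppose.

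Optional tidying, not correction of an error: add a cross-reference in Protocol 7.2 to Section 10.3.4.1, so that a stopped infusion is read as one terminated or not restarted.

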### Study Level Stopping Rules

An independent data monitoring committee (IDMC) will actively monitor the ongoing safety of patients and can make recommendations about early study closure or changes to the conduct of the study. The Sponsor may decide to stop or make changes to the study based on the recommendations of the IDMC.

A treatment arm may be discontinued if there is a clinically meaningful imbalance between treatment arms in any of the following safety criteria:

1. Incidence of SAEs
2. Incidence of AESIs
3. Progression of COVID-19 to more severe, critical or multi-organ dysfunction
4. Incidence of clinically significant recurrence of severe or critical disease after clinical improvement

### End of study definition

The end of study is defined as the date the last patient completes the last study assessment (in the hospital or via a follow-up phone call if the patient was discharged from the hospital before day 60), withdraws from the study, or is lost to follow-up (ie, the study patient can no longer be contacted by the investigator).

- A participant may withdraw from the study at any time at his/her own request, or may be withdrawn at any time at the discretion of the Investigator for safety, behavioral, compliance, or administrative reasons. This is expected to be uncommon.
- At the time of discontinuing from the study, if possible, an early EOS visit should be conducted.
- The participant will be permanently discontinued both from the study intervention and from the study at that time.
- If the participant withdraws consent for disclosure of future information, the Sponsor may retain and continue to use any data collected before such a withdrawal of consent to the extent allowed by local regulation.
- If a participant withdraws from the study, he/she may request destruction of any samples taken and not tested, and the Investigator must document this in the site study records.

If participants no longer wish to take the intervention, they will be encouraged to remain in the study.

The Investigators should discuss with them key visits to attend. The value of all their study data collected during their continued involvement will be emphasized as important to the public health value of the study.

Participants who withdraw from the study intervention should be explicitly asked about the contribution of possible AEs to their decision, and any AE information elicited must be documented.

All study withdrawals should be recorded by the Investigator in the appropriate CRF forms and in the participant's medical records. In the medical record, at least the date of the withdrawal and the reason should be documented.

In addition, a participant may withdraw his/her consent to stop participating in the study. Withdrawal of consent for intervention should be distinguished from withdrawal of consent for follow-up visits and from withdrawal of consent for non-participant contact follow-up, eg, medical record checks. The site should document any case of withdrawal of consent.

Participants who have withdrawn from the study cannot be rerandomized (treated) in the study. Their inclusion and intervention numbers must not be reused.

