## **7 DISCONTINUATION OF STUDY INTERVENTION AND PARTICIPANT DISCONTINUATION/WITHDRAWAL**

### **7.1 DISCONTINUATION OF STUDY INTERVENTION**

#### **7.1.1 Definitive discontinuation**

A patient has the right to withdraw from the study at any time, for any reason, and without repercussion.

The investigator and/or sponsor have the right to withdraw a patient from the study if it is no longer in the interest of the patient to continue in the study, or if the patient's continuation in the study places the scientific outcome of the study at risk (eg, if a patient does not or cannot follow study procedures). An excessive rate of withdrawals would render the study uninterpretable; therefore, unnecessary withdrawal of patients should be avoided.

Patients who opt to withdraw from the study may be asked to provide a final blood draw sample for PK analysis before withdrawing from the study.

Patients prematurely discontinued from the study will not be replaced.

In rare instances, it may be necessary for a participant to permanently discontinue (definitive discontinuation) study intervention. If study intervention is definitively discontinued, the participant will remain in the study to be evaluated for 60 days. See [Section 1.3](#) for data to be collected at the time of discontinuation of study intervention and follow-up and for any further evaluations that need to be completed.

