### **7.3 LOST TO FOLLOW UP**

A participant will be considered lost to follow-up if he or she repeatedly fails to return for scheduled visits and is unable to be contacted by the study site.

The following actions must be taken if a participant is discharged and cannot be reached by phone for the Day 60 EOS for a required study visit:

- The site must attempt to contact the participant and reschedule the missed visit as soon as possible and counsel the participant on the importance of maintaining the assigned visit schedule.
- Before a participant is deemed lost to follow up, the Investigator or designee must make every effort to regain contact with the participant (where possible, 3 telephone calls and, if necessary, a certified letter to the participant's last known mailing address or local equivalent methods). These contact attempts should be documented in the participant's medical record.
- Should the participant continue to be unreachable, he/she will be considered to have withdrawn from the study.

Discontinuation of specific sites or of the study as a whole are handled as part of Appendix 1 (Section 10.1).

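### Investigator or sponsor withdrawal from the whole study can leave a dosed patient's Day 29 survival and primary outcome uncollected, and the tracing steps in Section 7.3 are tied to Day 60 instead of Day 29

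*Protocol*

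**What the plan says.** **Withdrawal.** Protocol Section 7.2, under its End of study definition subheading, allows that a participant "may be withdrawn at any time at the discretion of the Investigator for safety, behavioral, compliance, or administrative reasons". It adds: "The participant will be permanently discontinued both from the study intervention and from the study at that time". Section 7.1.1 gives the investigator and the sponsor a parallel right, among other grounds "if the patient's continuation in the study places the scientific outcome of the study at risk", with failure to follow study procedures as the example.

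**What is collected afterwards.** Section 7.2 says: "At the time of discontinuing from the study, if possible, an early EOS visit should be conducted". Footnote 3 of the Schedule of Activities lets that assessment be brought forward when a patient withdraws. The text in 7.2 that separates stopping treatment, stopping visits and stopping record checks concerns the participant's own consent. Sections 8.3 and 8.3.3 keep the investigator responsible for following serious adverse events, AESIs, and events that led to discontinuation.

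**Stopping treatment only.** Section 7.1.1 provides: "If study intervention is definitively discontinued, the participant will remain in the study to be evaluated for 60 days".

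**Analysis.** The mITT set is every randomized and dosed patient, analyzed as randomized (Protocol Table 10; SAP 2.3.1.1). For the primary endpoint, a patient without improvement is censored at the last observation (Protocol 9.4.2; SAP 2.4.4.1). For Day 29 survival the SAP has no rule for unknown status. Its general rule in 2.5.3 leaves patients with missing categorical data out of percentages.

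**Tracing.** Section 7.3 introduces its contact steps with: "The following actions must be taken if a participant is discharged and cannot be reached by phone for the Day 60 EOS". The primary analysis is planned when the last randomized patient reaches Day 29 (Protocol 9.4; SAP Section 4).

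**The concern.** Treatment is one infusion on Day 1, with a possible second 24 to 48 hours later. Once dosing is over, a safety, behavioral, compliance or administrative reason may justify ending study procedures for a patient. None of these reasons in itself requires the trial to stop learning whether the patient is alive at Day 29. As written, withdrawal on any of these grounds ends follow-up as well.

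The patient remains in the primary analysis set, so the gap reaches both formally tested endpoints. Censoring at withdrawal treats the patient as having the same later chance of improvement as those who stay, and dropping unknown status from the survival percentage makes the same assumption about death. Neither assumption is safe if a withdrawal for safety reasons is linked to prognosis, and the comparison is distorted if such withdrawals are more frequent in one arm. Under Protocol 9.4.2 an unimproved patient who dies without rescue medication is censored at Day 29 and so stays in the risk set until then. An unimproved patient who is withdrawn leaves it at the last observation, which raises that arm's apparent improvement rate if the patient would have done badly.

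The Day 60 trigger in 7.3 adds a second route to unknown Day 29 status among discharged patients.

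**Working it through.** **1. The plan's own figure, and whether power is at stake.** Inputs from Protocol 9.2: 160 against 80 patients, 70% against 45% improved at Day 15, two-sided 0.05, power of at least 90%. With exponential times:

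- HR = ln(1 − 0.70) / ln(1 − 0.45) = 2.014.
- Events by Day 15 = 160 × 0.70 + 80 × 0.45 = 148.
- Schoenfeld: Φ(√(148 × 1/3 × 2/3) × ln 2.014 − 1.96) = 98.0%. Freedman with 2:1 allocation: Φ(√(148 × 2) × 1.014 / (1 + 2 × 2.014) − 1.96) = 93.4%. Both meet the stated bound.
- With 29 days of follow-up, about 199 events are expected and Schoenfeld power is 99.7%. If 5% of patients contributed nothing at all, power would be 99.5%; at 20%, 98.6%.

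So the issue is bias, not power.

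**2. Path of a dosed patient withdrawn before Day 29.**

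| Step | Rule | Result |
|---|---|---|
| Leaves study | 7.1.1 or 7.2 | No later contact required |
| Early EOS | 7.2; SoA footnote 3 | Only where feasible; gives status at withdrawal |
| Primary endpoint | SAP 2.4.4.1 | Event if already improved or discharged; otherwise censored at last observation |
| Day 29 survival | SAP 2.5.3 | Unknown status left out of the percentage |

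**3. Size for survival.** The documents give no withdrawal rate and no mortality for these patients. Assumed: 160 patients, 90% truly alive at Day 29, 40% mortality among those withdrawn, withdrawals in one arm only.

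- None withdrawn: 144/160 = 90.0%.
- 5 withdrawn (3%), of whom 3 survive: (144 − 3)/(160 − 5) = 141/155 = 91.0%.
- 10 withdrawn (6%), of whom 6 survive: (144 − 6)/(160 − 10) = 138/150 = 92.0%.

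The apparent gain is 1 to 2 points. A second assumed case takes 20% true mortality in both arms and withdraws 8 of 160 in one arm. If half of them die, observed mortality is (32 − 4)/152 = 18.4%; if 80% die, (32 − 6.4)/152 = 16.8%. The false benefit is 1.6 to 3.2 points.

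**4. Scale and limits.** The standard error of a 160 against 80 difference at 90% survival is √(0.9 × 0.1 × (1/160 + 1/80)) = 4.1 points, so a shift of 1 to 2 points is about 0.25 to 0.5 of a standard error. If both arms have the same withdrawal rate and prognosis, the difference hardly moves. With 5% unknown in each arm (8 and 4 patients) and no difference among known patients, best and worst cases put the true difference within ±5 points.

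**5. Tracing.** Assume uniform accrual over the planned 90 days. The share not yet at Day 60 when the database is locked L days after the last patient's Day 29 is (60 − 29 − L)/90.

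- L = 0: 31/90 = 34%.
- L = 14: 17/90 = 19%.
- L = 31: 0% at nominal Day 60.

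The documents give no value for L.

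**The case against.** **A reader might infer that 7.2 contradicts 7.1.1.** It does not. The 60-day rule in 7.1.1 governs a patient whose treatment is stopped; the bullets in 7.2 govern a patient who leaves the study. Section 7.2 also encourages patients who refuse further treatment to stay. What remains is that reasons which could be handled by stopping procedures alone may lead to full withdrawal.

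**A reader might infer that outcomes are routinely lost.** The documents do not support that. Section 7.2 anticipates few withdrawals, and 7.1.1 warns against unnecessary ones because too many would make the trial uninterpretable. Data up to withdrawal are kept, and an improvement or discharge already reached counts as an event. The risk is confined to patients withdrawn before Day 29.

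**Some withdrawn patients are still followed.** Sections 8.3 and 8.3.3 do extend follow-up for serious events, AESIs and events that caused discontinuation. This stands, but it follows an event to its resolution or stabilization. It does not collect Day 29 vital status for every withdrawn patient, and behavioral or administrative withdrawals need not involve any such event.

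**Survival is also shown by Kaplan-Meier curves and a Cox model** (SAP 2.4.4.2), which use the observed time. True, but the tested comparison is the CMH test of the Day 29 percentage, and those methods also assume non-informative censoring.

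**A reader might infer that about a third of patients lack tracing at the primary lock.** That figure needs a lock on the very day the last patient reaches Day 29. A missed Day 29 call affects survival only, because discharge already counts as a primary event, and a later Day 60 contact settles Day 29 status retrospectively. Section 7.3 also has a general sentence on efforts before declaring loss to follow-up, but its list is introduced by the Day 60 contact.

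**Conclusion.** The point holds as a gap in required follow-up. Investigator or sponsor withdrawal can end all follow-up of a dosed patient, no text then requires Day 29 vital status, and the analysis rules handle the missing outcome as though it were unrelated to prognosis. Bias in both tested endpoints requires that withdrawal differ by arm and be related to outcome. Under the assumed one-arm rates above, the effect on Day 29 survival is about 1 to 2 points. That is small against the sampling error, but it is avoidable and its direction would be unknown to the reader of the results. Primary power is not a concern.

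The tracing gap is separate and touches only the key secondary endpoint. The share of patients not yet at Day 60 at lock runs from about 34% to about 0% depending on the lock date, and only those among them who were discharged and missed the Day 29 call are affected.

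All withdrawal and mortality rates are assumptions. The illustration uses the planned 160 and 80; closing the 200 mg arm changes the split but not the argument. The change is worth making because it is cheap and protects both tested endpoints.

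**What to change.** - **Protocol 7.1.1 and 7.2:** state that withdrawal by the investigator or sponsor ends study procedures only. Vital status, discharge and readmission through Day 29 and Day 60 continue to be collected from the hospital record or by phone, unless the patient withdraws consent for that.
- **Protocol 7.3:** apply the existing tracing steps to a missed Day 29 call as well, to be completed before the primary lock.
- **SAP 2.4.4.2:** add a rule for unknown Day 29 status, with a sensitivity analysis such as the best and worst case bounds above.

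The cost is protocol and SAP wording and a few extra calls or record checks by sites that already make these calls. No visits are added, and the participant's right to withdraw consent is unchanged.
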